11.5 Archiving

Study documentation will be archived by the Co-Sponsors at the end of the trial for a minimum period of 25 years.

Medical notes will be archived in accordance with the principles outlined in NHS standard care guidance. As the medical notes are related to research there will be a requirement to retain them for a

period of 25 years. Involvement in the trial should be documented in the participant's medical notes by the local PI or delegated individual and clearly marked with 'do not destroy' and a retention date provided.

Archiving of Site Files will also be for a minimum of 25 years from completion of the trial, and this action will be delegated to the sites in the Clinical Trial Site Agreement that will be put in place between the Co-Sponsors and sites. Sites will be notified by the Co-Sponsors when site files can be archived. Destruction of site files can only take place with the approval of the Co-Sponsors.

12 MONITORING, AUDIT & INSPECTION

Monitoring will be conducted by NHS Greater Glasgow & Clyde (GG&C) monitor(s) in accordance with local SOPs. The level, frequency and priorities of monitoring will be based on the outcome of the completed sponsor and monitoring risk assessment, and will be clearly documented in the monitoring plan which will be approved by the NHS GG&C Research Governance Manager or Lead Clinical Trial Monitor. As standard, monitoring visit(s) will cover site file review, review of informed consent forms (ICFs), Source Data Verification (SDV) and Serious Adverse Event (SAE) review as per monitoring plan objectives.

13 ETHICAL AND REGULATORY CONSIDERATIONS

13.1 Research Ethics Committee (REC) review & reports

Before the start of the trial, the CI will seek favourable opinion from a Research Ethics Committee (REC) which has specific competence for adults with incapacity. The REC will review the trial protocol, Informed Consent Forms and other relevant documents.

Substantial amendments that require review by REC will not be implemented until the REC grants a favourable opinion for the amendment. It is noted that amendments may also need to be reviewed and accepted by the MHRA and/or NHS R&D departments before they can be implemented in practice at sites.

All correspondence with the REC will be retained and copies kept in the Trial Master File and Investigator Site Files.

An annual progress report will be submitted to the REC within 30 days of the anniversary date on which the favourable opinion was given, and annually until the trial is declared ended (this is the Chief Investigator's responsibility).

At the conclusion or early termination of the trial, it is the CI's responsibility to notify the REC and document any reasons for a premature termination, in accordance with HRA guidance. A final report will be prepared and submitted to the REC within one year of the conclusion of the trial and will include any publication of results.

13.2 Peer review

The application for funding the study was approved by the National Institute for Health and Care Research (NIHR) Health Technology Assessment (HTA) Programme.

13.3 Patient and Public Involvement and Engagement

The PPIE lead for the CLASP study is a stroke survivor with several years of experience of both public engagement and PPIE in stroke. She has had key leadership roles in previous NIHR-funded studies (STOPtoolkit and CHOSEN) with appropriate support and mentoring. She has shared her lived experience of stroke to undergraduates at the University of Manchester, led on stroke public

engagement activities (e.g. Brain Health Day, Manchester 2023 https://stroke-impact.org/brain-healthday/) and works closely with regional stroke support groups.

During the trial design and funding application, partnership with The Stroke Association's Stroke Voices in Research (SViR) Group ensured that the trial design includes the priorities and views of stroke survivors. Prior to the Stage 1 Application, a PPIE workshop (Workshop 1) was co-developed to establish how stroke survivors and their caregivers would contribute to the proposal. In advance of the workshop, PPIE priorities for the trial design were identified. Workshop 1 comprised 4 stroke survivors and 1 family caregiver and took place online. The PPIE group confirmed the need for a clinical trial, in terms of importance of the unmet need and poor prognosis of patients with stroke-associated pneumonia (PSP). The intervention, where some participants would get extra antibiotics but all participants would still get usual antibiotic and other stroke unit care was felt to be justified. The panel were reassured that randomisation into the trial would not result in delays to patients care. In the workshop, the group considered participant eligibility and how to obtain consent. It was acknowledged that the majority of participants would have relatively severe stroke and many would lack capacity so personal or professional consultee consent would be appropriate in view of the poor prognosis of PSP. Finally, trial outcome measures were discussed. The group felt that the modified Rankin Scale (mRS) was the most appropriate outcome measure, because improving functional outcome rather than reducing mortality alone was considered important. Other outcomes, for example relating to caregiver burden and time spent at home were proposed.

A second workshop was convened in partnership with the Stroke Association SViR group (Workshop 2) which included 5 stroke survivors and 1 family caregiver. In Workshop 2, the panel comments from Stage 1 were reviewed and it was agreed that a more stroke-related patient-reported outcome measure should be included. The Stroke Impact Scale is now included as a secondary outcome measure. The focus of Workshop 2 was how PPIE would contribute to the set-up, delivery and dissemination of the trial. This included in what form the PPIE panel would take, how many PPIE members would be required, ensuring diversity and inclusion, mentoring and training, the main tasks/roles and frequency and method of meeting.

A bespoke PPIE panel for the trial comprising 4 members in total (led by the PPIE lead stroke survivor co-applicant) will be convened. The importance of equality and diversity and balanced representation of age, sex, ethnicity and geography will be taken into account in the recruitment of membership. The PPIE panel will be supported by the trial management team and the Stroke Association SViR team, and will be offered appropriate training tailored to their requirements and needs. The panel will meet regularly (independent of the Trial Management Group (TMG)) to pool expertise, discuss progress pertinent to the PPIE agenda and review their activities and involvement, feeding back to the Chief Investigator and TMG. Specific roles of the PPIE panel will be to:

- 1. Undertake pro-active engagement with the TMG, which will include feeding back from (and into) the PPIE panel meetings and Trial Steering Committee. An important role will be to review trial recruitment progress to ensure diversity of the recruited participants and included sites and to liaise with regional PPIE groups to publicise the trial as needed.
- 2. Co-design participant information resources (e.g. Participant Information Sheets) in appropriate formats, including guidance for aphasia-friendly formats.
- 3. Participate in preparation of regulatory approvals, including attendance at ethics committee meetings to ensure the views and experiences of stroke survivors are incorporated.
- 4. Dissemination of the study at all stages including strategies to disseminate study results to participants and their families, the stroke community and wider public.

The SviR group felt strongly about consideration of alternative formats for dissemination, including use of social media, podcasts, websites, networks of regional stroke groups and relevant conferences and these will be explored.

13.4 Regulatory compliance

This study will not commence recruitment until the MHRA provides a Clinical Trial Authorisation and it has received a favourable opinion from the REC.

This Protocol and conduct of the trial will comply with the Medicines for Human Use (Clinical Trials) Regulations 2004 and all relevant amendments.

Prior to site commencing enrolment, the CI and the Principal Investigator or designee will apply for NHS permission from the site's Research and Development (R&D) department.

For any amendment that will potentially affect a site's NHS permission, the Chief/Principal Investigator or designee will confirm with that site's R&D department that NHS permission is ongoing (note that both substantial amendments, and amendments considered to be non-substantial for the purposes of REC and/or MHRA may still need to be notified to NHS R&D).

13.5 Protocol compliance

Prospective, planned deviations or waivers to the protocol are not allowed under the UK regulations on Clinical Trials and must not be used, e.g. it is not acceptable to enrol a participant if they do not meet the eligibility criteria or restrictions specified in the trial protocol.

While every effort must be made to comply with the approved protocol to demonstrate regulatory compliance, it is acknowledged that protocol deviations occur commonly with varying frequency in clinical trials. Protocol deviations are assessed based on their impact to patient safety, data integrity or trial integrity and must be adequately documented on the relevant forms and reported to the Chief Investigator and Sponsor immediately.

Deviations from the protocol which are found to frequently recur are not acceptable, will require immediate action and could potentially be classified as a serious breach.

13.6 Notification of Serious Breaches to GCP and/or the protocol

Serious breach to GCP and/or the protocol will be defined as a breach which is likely to effect to a significant degree:

- 1. The safety or physical or mental integrity of the participants of the trial; or
- 2. The scientific value of the trial.

If a breach occurs during trial conduct that fulfils either of these criteria, the sponsor must be notified immediately. The sponsor will notify the appropriate authorities in writing of any serious breach in accordance with their SOPs.

13.7 Data protection and participant confidentiality

All investigators and trial site staff must comply with the requirements of the Data Protection Act 2018 and the General Data Protection Regulation with regards to the collection, storage, processing and disclosure of personal information and will uphold the Act's core principles.

Personal information collected via the eCRF to enable Day 90 assessments to be carried out will be encrypted and held in a study database separate from the database containing other trial data. Signed informed consent forms will be scanned and securely uploaded into the eCRF and stored with restricted access for study monitoring purposes. Access will be limited to the trial monitoring team wherever possible but it may become necessary for other members of the trial team from NHS Greater Glasgow and Clyde and the University of Glasgow to access this data under certain exceptional circumstances. All members of the trial team are appropriately trained in the use of data collected from participants and will not access this data without reason.

All electronic data will be held securely in accordance with ISO 27001 at the Robertson Centre for Biostatistics, part of the Glasgow Clinical Trials Unit. All Centre staff are required to sign confidentiality agreements and to follow Standard Operating Procedures in accordance with Good Clinical Practice and ISO certification.

The trial data managers, statisticians, or any other staff who will perform data related tasks will only be able to access depersonalised data where the participant's identifying information is replaced by a unique study identifier.

Only those that have been trained and approved will be able to enter or view any data via the web portal. Each site can only see their own patients' data. Consent forms will be stored at the study site in a secure location accessible only to study teams.

13.8 Financial and other competing interests for the Chief Investigator, PIs at each site and committee members for the overall trial management

A log of financial or other competing interests for the CI, PIs and committee members will be held centrally by trial management throughout the trial. The Trial Coordinator will request this information at the site initiation visit and at regular intervals during study conduct, and it will be made available to the Sponsor.

13.9 Indemnity

The Co-Sponsors will ensure that provision has been made for insurance or indemnity to cover the liability of the investigator and sponsor which may arise in relation to the clinical trial in accordance with Part 2 (14) of Schedule 1 to SI 2004/1031.

The substantive employer of the Chief Investigator is the University of Manchester. Provision has been made to cover liability and indemnity for claims made by participants regarding design of the trial protocol, interactions with ethics committees and/or clinical trials authorisation process. Agreements between Co-Sponsors and the University of Manchester will be detailed in a collaboration agreement.

13.10 Amendments

Any change in the study protocol or REC-approved trial documents will require an amendment. Any proposed amendments will be initiated by the CI following discussion with the Sponsor and any required amendment forms will be submitted to the regulatory authority, REC and sponsor.

The sponsor will determine whether an amendment is non-substantial or substantial. All amended versions of the protocol will be signed by the CI and sponsor representative.

Following a substantial amendment, favourable opinion/approval must be sought from the original reviewing REC, MHRA (where appropriate) and Research and Development (R&D) office prior to implementation. The Chief Investigator will be responsible for informing the Trial Management Group of all protocol amendments.

13.11 Post trial care

Study treatment will occur for 5 days alongside participants standard care pathway. Upon completion of study treatment, participants will continue with standard clinical care and no provision for additional care is required.

13.12 Access to the final trial dataset

During the trial and in the period prior to publication of the main study results as described in the protocol, only GCTU will have access to the full dataset. After that period, the Trial Steering Committee will conduct further data analyses for a period of three years. After that time, the Trial

Steering Committee will consider requests from external parties for further analyses of the study data. Proposals that are scientifically well founded and have an academic basis and where relevant data extractions and analyses are appropriately funded will not be refused. These will be considered as collaborative exercises where the contributions related to study design, conduct, database creation and maintenance and data analysis will be recognised in authorship of any scientific publication. The approach we will take will be to minimise any possibility of breach of participant confidentiality. Normally this will be achieved by minimising data travel. However, for the purposes of individual patient meta-analysis and other reasons, data may be transferred to other sites. Such transfer will require assurances on information security systems at the sites that data are to be transferred to and will involve a legal data transfer agreement. A log of all data requests and subsequent data transfers will be held at GCTU.

14 DISSEMINIATION POLICY

14.1 Dissemination policy

The study database will be owned by the University of Glasgow and maintained on behalf of the study investigators, represented by the Trial Steering Committee as it is constituted during and after the trial.

The study protocol and a description of the recruitment experience and participant baseline characteristics will be published before study completion. On completion of the trial, the database will be locked and analysed by staff of the Robertson Centre for Biostatistics, University of Glasgow. A final study report will be prepared and the results will be published in a major medical journal.

For the participating patients, the stroke community and wider public, the progress and complete trial results will be reported to a range of user platforms such as PPIE groups, conferences and on social media. Findings will also be published to a range of websites such as the Stroke Association and Stroke Voices in Research.

14.2 Authorship eligibility guidelines and any intended use of professional writers

The main results of the study will be compiled, written up and published by the study grant holders and others taking responsibility for the study results (e.g. the statistician conducting the final analysis) on behalf of the CLASP investigators. The CLASP investigators will include all site PIs, all committee members and key members of relevant study coordinating groups (including the Sponsor and GCTU). A separate publications policy will be developed.

No professional writers will be used. All grant holders will be included as authors on the main trial publication, provided they meet the International Committee of Medical Journal Editors authorship criteria for manuscripts submitted for publication. Additional authors can be added if they meet these criteria.

16. APPENDICES

Appendix 1: Definition of women of childbearing potential and contraception requirements

Women of childbearing potential

Women of childbearing potential are defined as those who have experienced menarche; AND not undergone successful surgical sterilisation (hysterectomy, bilateral salpingectomy, or bilateral oophorectomy); AND are not post-menopausal i.e. amenorrhea for ≥12 consecutive months (without another medical cause).

Contraception requirements

Highly effective contraception: Defined as those that can achieve a failure rate of less than 1% per year when used consistently and correctly OR

Such methods include:

- combined (oestrogen and progestogen containing) hormonal contraception associated with inhibition of ovulation
 - oral¹
 - intravaginal
 - transdermal
- progestogen-only hormonal contraception associated with inhibition of ovulation¹
 - oral
 - injectable
 - implantable
- intrauterine device (IUD)
- intrauterine hormone-releasing system (IUS)
- bilateral tubal occlusion

Other contraception methods with a failure rate of more than 1% per year

- progestogen-only oral hormonal contraception, where inhibition of ovulation is not the primary mode of action¹
- male or female condom with or without spermicide
- cap, diaphragm or sponge with spermicide

A combination of male condom with either cap, diaphragm or sponge with spermicide (double barrier methods) are also considered acceptable

1. Patients taking oral contraceptives should be warned that if diarrhoea, vomiting or breakthrough bleeding occur there is the possibility of contraceptive failure.

Appendix 2: Prohibited concomitant medicines

This list is not exhaustive but is based on drugs listed as contraindicated in the SmPC, as 'manufacture advises avoid' in the BNF, and additional drugs identified by the Sponsor to maximise safety. Please refer to the relevant Summary of Product Characteristics or contact the Sponsors for further advice.

| Prohibited Medicines |
|--|
| Abemacicib |
| Alprazolam |
| Amiodarone |
| Anti-arrhythmic drugs (e.g. Quinidine) Astemizole, |
| Atypical antipsychotics (e.g. quetiapine) Avanafil |
| Avapritinib |
| Axitinib |
| Bedaquiline |
| Cabergoline |
| Carbamazepine |
| Cariprazine |
| Ciclosporin |
| Chloroquine |
| Cisapride |
| Colchicine |
| Crizotinib |
| Daridorexant |
| Darifenacin |
| Disopyramide |
| Domperidone |
| Dronedarone |
| Eletriptan |
| Ergometrine |
| Ergot alkaloids – ergotamine and dihydroergotamine |

| Prohibited Medicines |
|---|
| (cont) Everolimus |
| Fidaxomicin |
| Fineronone |
| Grazoprevir |
| HIV infection drugs. e.g. efavirenz, nevirapine, saquinavir, ritonavir, atazanavir, zidovudine Hydroxychloroquine |
| Ibrutinib |
| Irinotecan |
| Itraconozole |
| Ivabradine |
| Lapatinib |
| Lercanidipine |
| Lomitapide |
| Lurasidone |
| Methadone |
| Midazolam |
| Mizolastine |
| Mobocertinib |
| Naloxegol |
| Nilotinib |
| Phenytoin |
| Pimozide |
| Pimozide |
| Quetiapine |
| Ranolazine |

| Prohibited Medicines (cont) |
|--|
| Reboxetine |
| Rifabutin |
| Rifampicin |
| Rifapentine |
| Rimegepant |
| Rupatadine |
| Salmeterol |
| Phosphodiesterase 5 inhibitors e.g. sildenafil, tadalafil, vardenafil. This applies to concurrent use only. Sirolimus |
| Statins / HMG CoA enzyme reductase inhibitors. |
| For purposes of this study, all statins are contraindicated Tacrolimus |
| Temsirolimus |
| Tepotinib |
| Terfenadine |
| Theophylline |
| Ticagrelor |
| Tolterodine |
| Valproate |
| Vardenafil |
| Verapamil |
| Vinblastine |
| Voclosporin |

Appendix 3: Medicines with known interactions with clarithromycin but may be used with caution at investigator's discretion

| Medicines where there may be drug interactions and caution is advised | Comments | | |
|---|---|--|--|
| Direct acting oral anticoagulants e.g. dabigatran, rivaroxaban, apixaban and edoxaban | Use concurrently with caution and consider individual risk of bleeding. | | |
| Warfarin | Risk of serious haemorrhage and significant elevations in International Normalised Ratio (INR) and prothrombin time when clarithromycin is co- administered with warfarin. INR and prothrombin times should be frequently monitored while patients are receiving clarithromycin and oral anticoagulants concurrently. | | |
| Calcium channel blockers eg. amlodipine, diltiazem (note verapamil which is prohibited) | Risk of hypotension. Monitor blood pressure during concurrent use. | | |
| Digoxin | May increase digoxin concentrations. Measure digoxin levels during concurrent use. | | |
| Insulin | Risk of hypoglycamia. Monitor glucose levels carefully during concurrent use. | | |
| Oral hypoglycaemic agents eg, sulphonylurea, nateglinide repaglinide | Risk of significant hypoglycamia. Monitor glucose levels carefully during concurrent use. | | |
| Corticosteroids | Potential for increased systemic exposure to corticosteroid. Monitor closely for corticosteroid undesirable effects. | | |
| Omeprazole | May increase omeprazole concentrations. Suggest review if concurrent use is needed and use alternative agent. | | |
| Cilostazol | May alter cilostazole concentrations. Should be withheld during duration of clarithromycin use. | | |
| Oral contraceptives | If diarrhoea, vomiting or breakthrough bleeding occur there is a possibility of contraceptive failure. Women of childbearing potential should use other forms of contraception during clarithromycin use. | | |

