8.9 Concomitant medication

A participant's concomitant medication should be checked by a medically qualified investigator before randomisation to ensure eligibility and to ensure appropriate action is taken regarding concomitant medication.

Participants prescribed or taking prohibited medicines as listed in Appendix 2 are ineligible for the study unless in the investigator's opinion the interacting medicine can safely and appropriately be withheld for the duration of clarithromycin treatment plus 3 days. Should an indication for these drugs develop during the study treatment period and treatment with a prohibited medicine commence, participants must be withdrawn from study clarithromycin treatment. Participants will also permanently stop trial clarithromycin treatment should clarithromycin (or other macrolide) become clinically indicated for antibiotic treatment as per local antimicrobial policies. Relevant data should continue to be collected on participants providing consent is still in place.

Participants prescribed or taking medication listed in Appendix 3 can be enrolled in the study at investigator discretion following consideration of advice contained in the protocol, the BNF and the SmPC.

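### The Appendix 3 row that allows calcium channel blockers excepts only verapamil, but Appendix 2 also prohibits lercanidipine

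*Protocol*

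**What the plan says.** Appendix 2 of the protocol lists prohibited concomitant medicines, mostly by individual name. "Lercanidipine" is one entry and verapamil is another.

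Appendix 3 lists medicines that interact with clarithromycin but may be used with caution at the investigator's discretion. One of its rows is "Calcium channel blockers eg. amlodipine, diltiazem (note verapamil which is prohibited". The comment beside it is "Risk of hypotension. Monitor blood pressure during concurrent use".

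Section 8.9 attaches different consequences to the two lists:

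- **Appendix 2:** "Participants prescribed or taking prohibited medicines as listed in Appendix 2 are ineligible for the study unless" the investigator judges that the drug "can safely and appropriately be withheld for the duration of clarithromycin treatment plus 3 days". If such a drug is needed during the study treatment period and "treatment with a prohibited medicine commence, participants must be withdrawn from study clarithromycin treatment".
- **Appendix 3:** patients taking a listed medicine "can be enrolled in the study at investigator discretion following consideration of advice contained in the protocol, the BNF and the SmPC".

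Section 8.8 likewise describes Appendix 3 as the list of interacting medicines that may be given together with clarithromycin at the investigator's discretion.

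Section 2.1.1 first states that contraindicated drugs must be stopped or withheld, and points to Appendix 2. Later in the same discussion it says that calcium channel blockers are allowed because they can be monitored in routine practice. It names no exception.

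**The concern.** Lercanidipine is a calcium channel blocker. The Appendix 3 row is a class entry, with amlodipine and diltiazem given only as examples, so on its face it covers lercanidipine. Its note removes verapamil and nothing else. A reader who sees one stated exception will naturally take the rest of the class as allowed. A row with no note would mislead less.

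The layout adds to this. Appendix 2 has no calcium channel blocker heading, although statins, phosphodiesterase 5 inhibitors and atypical antipsychotics have class entries there. Someone who searches by class finds only the Appendix 3 row and the sentence in section 2.1.1, and both permit use.

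The risk is that an investigator relies on the Appendix 3 row and gives lercanidipine alongside clarithromycin, with blood pressure monitoring in place of withholding. Sites could also apply different rules to the same drug. Section 5 plans at least 45 units, so the written lists need to give one answer.

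**Working it through.** There is no figure in the plan to reproduce. The check compares the texts and then works out how far apart the two instructions are.

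**Inputs**

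- Calcium channel blockers named in Appendix 2: lercanidipine and verapamil, so 2.
- Calcium channel blockers noted as prohibited in the Appendix 3 row: verapamil, so 1.
- Rows in Appendix 3: direct oral anticoagulants, warfarin, calcium channel blockers, digoxin, insulin, oral hypoglycaemics, corticosteroids, omeprazole, cilostazol and oral contraceptives, so 10. Rows carrying a prohibited-drug note: 1, this one.
- Clarithromycin course: 5 days, with 10 doses allowed over at most 7 days if doses are missed (section 8.6).
- Withholding rule: clarithromycin treatment plus 3 days (section 8.9).

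**The two rules applied to lercanidipine**

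| Situation | Appendix 2 with 8.9 | Appendix 3 with 8.8 and 8.9 |
|---|---|---|
| Taking it at screening | Ineligible unless it can be withheld | May be enrolled at investigator discretion |
| During clarithromycin | Withheld | May be co-administered, blood pressure monitored |
| Started during treatment | Clarithromycin withdrawn | No withdrawal required |

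Section 7.9.1 softens the last Appendix 2 entry: withdrawal applies where the prohibited medicine has not been temporarily discontinued by the local investigator.

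**Days off lercanidipine, per affected patient in the clarithromycin arm**

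Days withheld = days of clarithromycin + 3.

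- Standard course: 5 + 3 = 8 days.
- Dosing extended to the maximum: 7 + 3 = 10 days.
- Appendix 3 row: 0 days.

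**Which list is meant to prevail**

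Section 8.9 uses mandatory language for Appendix 2. Use of an Appendix 3 drug is discretionary and follows consideration of the protocol, the BNF and the SmPC. Section 2.1.1 states the prohibition before it allows the class. All of this suggests that Appendix 2 is meant to govern. However, no sentence says that an Appendix 2 entry overrides an Appendix 3 class row.

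**The case against.** The best reply is that Appendix 3 never names lercanidipine, whereas Appendix 2 does, and a named prohibition ordinarily beats a general class entry. The rest of the protocol supports that reading. The exclusion criteria on interacting medicines in section 6.2 point to Appendix 2 and not to Appendix 3. Section 7.9.1 ties withdrawal of clarithromycin to Appendix 2. Section 13.5 bars waivers of eligibility. Section 8.9 recognises only one way around an Appendix 2 listing, which is withholding the drug. It also says that concomitant medication "should be checked by a medically qualified investigator before randomisation to ensure eligibility", so the error does harm only if that investigator reads the caution list without the prohibited list. The sentence in section 2.1.1 is risk rationale. It does not except verapamil either, so it was hardly written as a list of exceptions.

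Most of this stands. It settles which list should win, limits the practical risk and keeps the severity low. It does not make the Appendix 3 note correct. The sponsor saw that this row needed an exception and wrote one that is incomplete, in a table that investigators use to decide on co-administration. If relied on, the row leads to the wrong action. Since section 2.1.1 is rationale, the edit there is for clarity; the Appendix 3 row is the correction that matters.

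**Conclusion.** The inconsistency is real. Of the 2 calcium channel blockers that Appendix 2 names as prohibited, 1 is carried into the Appendix 3 exception. For lercanidipine, the lists differ between 8 to 10 days of withholding and none, and between conditional ineligibility and discretionary enrolment.

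This measures a difference between instructions and is not an estimate of harm. The protocol gives neither the number of patients taking lercanidipine nor the specific reason for prohibiting it, so neither is estimated. The conclusion rests on one fact that the protocol does not state, the basic classification of lercanidipine as a calcium channel blocker. The sponsor's decision to prohibit the drug is not questioned.

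This is a low-severity wording error that should be corrected. It bears on patient safety and uniform conduct across sites, and has no effect on sample size, error rate or the primary analysis.

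**What to change.** - **Appendix 3, calcium channel blocker row:** change the note to say that verapamil and lercanidipine are both prohibited.
- **Section 2.1.1, sentence allowing calcium channel blockers:** add *except those listed in Appendix 2*.
- **Clinical Information Sheet (described in section 8.6):** align it if it repeats the row. The sheet is not among the documents, so this is a conditional check.

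The cost is one table row and one sentence, plus the sheet if it is affected. Nothing in the trial's design, size or analysis changes.
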